5.3. Per protocol analysis set

The per protocol (PP) analysis set includes subjects in the FAS without any major protocol deviations that could confound the interpretation of analyses conducted on the FAS. Major protocol deviations will be defined prior to database lock and without knowing the treatment of individual cases. Patients taking less than 80% of the prescribed medication will be excluded from the PP set. Patients that fail to provide a minimum 80% of endpoint data will also be excluded from per-protocol analysis from that particular endpoint.

Any per-protocol analysis would be limited to the primary and efficacy/symptom-based secondary endpoints as defined in Sections 6.2 & 6.3.1.

5.4. Extended analysis set

The extended analysis set expands on the FAS by including any subject who completed the study, regardless of whether they had confirmed RV-16 infection. The set will be used to investigate pre-infection mechanistic effects of OC459 and will also be used for any *ex-vivo* analyses.

6. Variables of Analysis

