4.4 WITHDRAWAL CRITERIA

Participants will be free to discontinue trial medications at any point during the study without giving reason. Where possible, follow up will continue. If a participant chooses to withdraw consent, data up to the point of self-withdrawal will be included unless the participant chooses otherwise.

Investigators will withdraw any subject if they are unable to tolerate the study medications, or if the a research investigator feels this is necessary or appropriate. In all cases, the reason for withdrawal must be recorded on the case report form and in the subject's medical records. Subjects will be closely monitored by the Clinical Research Fellow. This is defined further in the section on 'Serious Adverse Events'.

Subjects who are considered evaluable (i.e. confirmed rhinovirus infection) with sufficient data to assess the primary endpoint (i.e. complete diary cards of symptoms up to day 14 post-rhinovirus infection) will be included in the analysis. Subjects who are either withdrawn from the trial or who chose to discontinue participation and do not meet these criteria will be replaced until a sufficient number of evaluable subjects are reached (n=20).

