5.2. Full analysis set

The full analysis set (FAS) includes subjects who:

- Are randomised into the study (D-21)
- Have been inoculated with the rhinovirus serotype 16 (RV-16) challenge virus (D0)
- Have confirmed RV-16 infection, defined as either (i) positive RV-16 PCR in nasal lavage at any time after inoculation (D0) or (ii) seroconversion (positive antibodies to RV-16 at a titre of at least 1:4 at the final study visit)
- Have completed at least 14 days post inoculation with RV-16.

These subjects are defined as 'evaluable' and form the basis of the power calculation.

The FAS will be used to assess the primary objective and will be used to analyse all efficacy endpoints plus any post-infection mechanistic outcomes.

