7.4. Exploratory Analysis

7.4.1. Exploratory Mechanistic Testing

Analysis to investigate any difference in effect of OC459 and placebo for the exploratory analyses below will be performed using the difference in values via unpaired (two-sample) t-test or Mann-Whitney U tests for non-parametric data.

- Changes in inflammatory cell counts by flow cytometry after drug treatment but before virus inoculation (for blood and nasal samples, not bronchial): Day -21 to Day -8.
- Changes in soluble mediators after drug treatment but before virus inoculation (nasal samples): Day -21 to Day 0.
- Changes in cell counts from bronchial biopsies taken at Day -8 and Day 5 will also be assessed CRTH2+ cells (cells/mm² tissue) & EG2+ activated eosinophils (cells/mm² tissue).

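### The set for the exploratory pre-inoculation tests should be defined by having the samples, not by what happens to the subject afterwards

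*SAP*

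**What the plan says.** SAP 5.4 gives the entry rule: "The extended analysis set expands on the FAS by including any subject who completed the study". Confirmed infection is not needed for this second route. The section then gives the purpose: "The set will be used to investigate pre-infection mechanistic effects of OC459". The same set serves the ex vivo analyses.

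Entry through the FAS (SAP 5.2) requires randomisation, inoculation, confirmed RV-16 infection and a follow-up condition: "Have completed at least 14 days post inoculation with RV-16". Infection is confirmed either by PCR on nasal lavage or by antibodies at the final study visit.

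SAP 7.4.1, under exploratory mechanistic testing, lists two comparisons that end before the virus is given:

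- The first takes cell counts, with this window: "after drug treatment but before virus inoculation (for blood and nasal samples, not bronchial): Day -21 to Day -8".
- The second takes the mediators measured in the nose, and the SAP words it as follows: "Changes in soluble mediators after drug treatment but before virus inoculation (nasal samples): Day -21 to Day 0".

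Two protocol statements bear on who should be analysed. Under Protocol 4.4, if a participant withdraws consent, "data up to the point of self-withdrawal will be included unless the participant chooses otherwise". Protocol 10.2, in contrast, restricts statistical analysis to subjects with confirmed infection.

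**The concern.** The outcome of these tests is complete at Day -8 or Day 0. Membership of the set is settled later, at Day 14 for the FAS route or at completion for the other route. Nothing that happens after the second sample can change a Day -21 to Day -8 or Day 0 difference. The completion condition therefore adds no information about the outcome, and the SAP gives no reason for it.

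It can do harm in two ways. It discards observed data from a trial of only 44 subjects. It also gives up part of the protection of randomisation, because leaving can depend on treatment. The run-in is spent on OC459 or placebo (Protocol 9.1). Rhinitis symptoms, an exacerbation or a viral illness in the run-in are exclusion criteria (Protocol 4.3), and investigators withdraw subjects who cannot tolerate the medication (Protocol 4.4). If such exits differ between arms and are related to the airway inflammation being measured, the remaining subjects are no longer a clean randomised comparison.

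The SAP has already accepted the principle. It waives infection status for these tests, presumably because infection has no bearing on a pre-infection effect. Later completion has no more bearing on it.

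**Working it through.** **Who is dropped with the outcome observed**

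- Leaves between Day -8 and Day 0: has both cell samples, has no Day 0 mediator sample, and is in neither set.
- Inoculated, leaves before Day 14, infected or not: has both cell samples and normally both mediator samples, and is in neither set.
- PCR-negative, passes Day 14, lost before the final visit: seroconversion cannot be read, so the subject is not in the FAS, and has not completed.
- PCR-positive, passes Day 14, lost before the final visit: is in the FAS, so is kept.
- Leaves before Day -8: has no second sample, so nothing observed is lost.

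Neither document defines completion for an individual. Protocol 9.1 puts the final visit at Day 42, and Protocol 3 gives 9 weeks from randomisation (Day -21 to Day 42 is 63 days), so Day 42 is the natural reading. If Day 14 were meant, the third group would be kept and the first two would still be lost.

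The protocol foresees such exits: section 12.8 sets pro rata payments for leaving after the first bronchoscopy (Day -8) and after inoculation (Day 0).

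**The plan's own figures**

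Inputs from Protocol 10.1 and SAP 4.4: SD 21.15, difference 22.21 (read as a raw difference), alpha 5%, power 80%, infection success 80%, 22 enrolled per arm. SAP 7.2 makes the test two-sided.

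- Evaluable per arm: 2 x [21.15 x (1.960 + 0.842) / 22.21]^2 = 14.24, rounded up to 15. The stated figure is reproduced.
- Allowing for infection success: 15 / 0.80 = 18.75, or 19 rounded up.
- Drop-out needed to reach 22: 1 - 19/22 = 13.6%, or 1 - 18.75/22 = 14.8% without rounding.

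The documents state no drop-out rate, so this 14-15% is back-solved. It describes loss of evaluable subjects; applying it to completion among all 44 is an assumption.

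**Size of the loss**

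Completers = 44 x (1 - drop-out). The largest possible ratio of standard errors is sqrt(44 / completers). It is reached only if every drop-out leaves after the second sample and none is in the FAS.

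| Drop-out | Outside the set | Completers | Largest SE ratio |
|---|---|---|---|
| 5% (assumed) | 2.2 | 41.8 | 1.026 |
| 10% (assumed) | 4.4 | 39.6 | 1.054 |
| 13.6% (implied) | 6.0 | 38.0 | 1.076 |
| 14.8% (implied) | 6.5 | 37.5 | 1.083 |
| 20% (assumed) | 8.8 | 35.2 | 1.118 |

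The lower limit in every row is no loss, because all drop-outs could leave before the second sample. In terms of power, the standardised difference detectable at 80% is (1.960 + 0.842) x sqrt(2/n): 0.84 at 22 per arm and 0.91 at 19 per arm.

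These counts refer to 44 randomised. Replacement of non-evaluable subjects (Protocol 4.4, SAP 4.7) could raise both the number randomised and the number dropped.

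**The case against.** The strongest reply is that little hangs on this. The tests are exploratory, SAP 7.3.1 and 7.3.2 already call for more caution with exploratory results, and the primary and secondary efficacy analyses use the FAS. That is correct and limits the weight of the point. It does not supply a reason for the completion condition.

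A second reply is that some exclusions are sensible. A viral illness, an exacerbation or rhinitis symptoms in the run-in could themselves alter nasal and blood cells and mediators. This has force, but those events happen on randomised treatment, so omitting the subjects belongs in a sensitivity analysis rather than in the definition of the set.

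Four stronger readings are tempting and are not supported:

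- A reader might infer that SAP 5.4 flatly contradicts the protocol. The Protocol 4.4 sentence concerns participants who withdraw consent and does not say which analysis their data enter. It does not expressly cover investigator withdrawals or losses to follow-up. Protocol 10.2 points the other way, and against it SAP 5.4 is the more inclusive rule. The tension lies partly within the protocol.
- A reader might infer that everything analysed in the extended set is finished by Day 0. That is not established for the ex vivo work: brushings are also taken on Day 5, blood is drawn then too, and SAP 7.4.2 names no visit.
- A reader might take six subjects, or 8%, as the expected loss. It is a ceiling at a back-solved rate.
- A reader might extend the argument to post-infection endpoints finished before Day 14, such as the Day 5 bronchial samples or Day 7 PC20. Those belong to the FAS, whose 14-day rule defines evaluability and underlies the sample size; nothing here supports changing it.

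**Conclusion.** The point holds for the two pre-inoculation comparisons in SAP 7.4.1. Randomised subjects whose outcome is fully observed are left out because of later events that treatment may influence, and no purpose is served.

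At the implied 14-15% drop-out, 0 to about 6 of 44 subjects and 0 to about 8% in standard error are at stake; over an assumed 5-20%, 0 to about 9 subjects. This rests on reading completion as attending the final visit and on applying the back-solved rate to all randomised subjects. Neither the direction nor the size of any bias can be derived from the documents. The matter is mainly one of selection after randomisation, and less one of power. The primary and secondary efficacy analyses are not touched.

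**What to change.** In SAP 5.4, define the set for the SAP 7.4.1 pre-inoculation tests as all randomised subjects who took at least one dose and have both the Day -21 sample and the relevant later sample (Day -8 for cells, Day 0 for nasal mediators), regardless of inoculation, infection or completion, unless the participant refused use of the data. SAP 5.1 already uses the randomised-and-dosed base for safety.

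Add a sensitivity analysis that omits subjects excluded for viral illness, exacerbation or rhinitis symptoms in the run-in. For the ex vivo work, include subjects who have the relevant cell sample, and state the visit it comes from.

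Reconcile Protocol 4.4 (data before self-withdrawal are kept) and Protocol 10.2 (infected subjects only) with the revised SAP 5.4. Leave the FAS rule for post-infection endpoints as it is.

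The cost is a few sentences and minor extra analysis work, with a denominator that varies slightly by endpoint and must be reported. No new data, visits or subjects are needed.

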6.1. Baseline Demographic Variables

- Gender
- Ethnicity
- Age (at enrolment)
- Height, weight & BMI
- Duration of asthma
- History of previous oral steroids
- Skin prick test: (a) which allergens (b) cumulative wheal size in mm²
- Smoking history +/- pack years
- Baseline asthma medications (this includes the ICS dose)
- Values of the following at screening and, in supplementary tables, at randomisation (day -21) and at visit 4 (day 0):
 - ACQ-6
 - FEV₁ + reversibility
 - FVC
 - FeNO
 - PC₂₀
 - Blood eosinophils
 - Serum IgE
 - Serum vitamin D (screening and randomisation only)

6.2. Primary Analysis Variable

- The primary endpoint will consist of the sum of uncorrected lower respiratory symptom scores from day 0 to day 14. Daily scores will be out of 21 (seven symptom questions rated from zero to three) creating a potential maximum total score of 315.

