1.2 RATIONALE FOR CURRENT STUDY

Hypothesis: This trial is designed to investigate the hypothesis that CRTH2 antagonism can prevent or attenuate the deterioration in symptoms in patients with asthma (i.e. asthma exacerbations) following rhinovirus infection.

Rationale for using the RV-induced asthma exacerbation model

The RV-induced asthma exacerbation model offers the ability to investigate treatment effects on exacerbations with a small number of volunteers, minimising the numbers exposed to a novel agent with limited safety data. In contrast, trials of therapies powered to evaluate an effect on naturally occurring exacerbations require several hundred volunteers, a long study period to capture enough events and are significantly more expensive to carry out.

The RV-induced exacerbation model has been used extensively around the world over >15 years, including four studies by [name] group [9, 10, 14, 15], and is well-established with an excellent safety profile (reviewed in [16]); across the studies at Imperial there have been no adverse events, and no need for hospitalisation or systemic corticosteroids during the infection. Moreover, the RV-induced exacerbation model uniquely provides the opportunity to select a well-defined sample population, use a uniform viral challenge, and sample repeatedly as the exacerbation evolves, allowing accurate dissection of the timings of responses and their relationship to viral load.

Rationale for using the CRTH2 antagonist OC459

As of August 2013, at least 12 CRTH2 antagonists were in active clinical development [17]. Of these, OC459 (Atopix Therapeutics Ltd) had been trialled for the longest duration in a phase 2 study (17 weeks). In total, 637 patients across five published studies have been exposed to OC459 [18-22], including 482 patients with asthma, with an excellent safety record. OC459 has therefore been chosen for further study from the available CRTH2 antagonists due to its safety profile; there is no reason to think that is more or less effective than any other CRTH2 antagonist.

In addition, the largest study of OC459 to date suggested that it may be effective in reducing exacerbations: a trend towards reduction in asthma exacerbations was noted, with a 3.8% incidence in the pooled dose groups compared to 7.7% on placebo ($p=0.107$) [22]. A dose of 25 mg once daily was as effective as the other doses (100mg twice daily and 200mg once daily) in this study.

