9 ASSESSMENT AND FOLLOW-UP

9.1 SUMMARY OF STUDY ASSESSMENTS AND PROCEDURES

After screening and providing informed consent, eligible participants will undergo baseline investigations and randomisation, followed by a 21 day run-in period on placebo or OC459. Towards the end of this period they will have a baseline bronchoscopy and other investigations. At the end of the run-in period, subjects will have a further set of investigations prior to rhinovirus inoculation the same day. Regular sampling and assessments will take place as indicated whilst treatment administration continues uninterrupted for a further 14 days, for a total of 5 consecutive treatment weeks. Trial medications are then stopped (day 14). Subjects will attend for a final follow-up visit 4 weeks later with convalescence investigations (day 42). Table 1 summarises subject visits and procedures during the study. Details of the individual study procedures are listed below.

Study participants will be seen frequently during the study period, daily if they wish. They have details to contact the Clinical Research Fellow and Clinical Research Nurse, and will be offered daily telephone contact. In this way participants will be assessed regularly by the investigating team and any adverse events detected rapidly. When the study is completed, subjects will return to the care of their GP (they will not be routinely followed-up by the study group).

	Screening visit 1	Screening visit 2	Visit 1 (baseline)	Visit 2	Visit 3	Visit 4	Visit 5	Visit 6	Visit 7	Visit 8	Visit 9	Visit 10	Visit 11
Study day			-21	-9	-8	0	2	3	4	5	7	10	42
Ideal weekday			F	W	T	F	Su	M	T	W	F	M	F
Visit length	30 min	60 min	60 min	45 min	3 hr	60 min	45 min	45 min	45 min	3 hr	60 min	45 min	30 min
Skin prick test	X												
Viral serology	X												X
Asthma Control Questionnaire (ACQ)	X		X	X		X						X	X
Spirometry (in clinic)	X		X	X		X	X	X	X	X	X	X	X
Histamine challenge (PC ₂₀)		X	X	X							X		
Exhaled nitric oxide (FeNO)		X	X	X		X		X		X	X	X	X
Blood tests		X	X		X			X		X		X	X
ECG		X											
Urine pregnancy test		X											
Chest radiograph		X											
IMP or placebo administration			Daily from day -21 → day 14 (then stop)										
Nasosorption			X			X	X	X	X	X	X	X	
Nasal lavage			X			X	X	X	X	X	X	X	
Nasal scrape			X		X			X		X			
Bronchoscopy (bronchosorption, BAL, brushings, biopsies)					X					X			
Sputum induction			X	X					X		X		
Virus inoculation						X							

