9.4 CLINICAL SYMPTOM SCORES (INCLUDING ACQ)

Patients will be required to keep a diary card of both upper and lower respiratory tract symptoms during the study period (see Appendices). The diary cards will be commenced 21 days prior to inoculation (on day -21) to derive a baseline symptom score. Symptom scores will be kept daily for 6 weeks post-inoculation until the convalescent visit. Spirometry measurements and drug compliance will be recorded on the same diary cards.

Upper Respiratory Tract Symptoms

The diary card of upper respiratory tract symptoms will be started 21 days prior to inoculation. A total upper respiratory clinical symptom score will be derived using a scale of 0 to 3 (absent, mild, moderate and severe) for each of the following eight respiratory symptoms: sneezing, headache, malaise, fever/chills, nasal discharge, nasal obstruction, sore throat and cough, according to previously established criteria [23]. Symptoms will be recorded at the same time of day and before any procedures such as bronchoscopy are performed. An example is shown below:

Symptom	Day 1	Day 2	Day 3	Day 4	Day 5	Day 6	Day 7
Sneezing							
Headache							
Malaise							

Fever/chills							
Nasal discharge							
Nasal obstruction							
Sore throat							
Cough							
Total score							

0 = absent, 1 = mild, 2 = moderate, 3 = severe

The maximum clinical severity score on any one day would be 24. Individual symptom scores will be accumulated over the six-day period from the onset of the cold and the recording on the day prior to inoculation subtracted. Thus, for a patient who has a score of zero on day -1 prior to inoculation, the maximum cumulative score for the six days is 144.

Lower Respiratory Tract Symptoms

A diary card of lower respiratory tract symptoms will be completed with a scoring system as outlined below:

Symptom	Day 1	Day 2	Day 3	Day 4	Day 5	Day 6	Day 7
Cough on waking							
Wheeze on waking							
Daytime cough							
Daytime wheeze							
Daytime breathlessness							
Nocturnal cough, wheeze, breathlessness							
Total score							

0 = absent, 1 = mild, 2 = moderate, 3 = severe

An exacerbation of asthma is defined as an increase in the total respiratory score of at least 2 points over baseline on 2 consecutive days.

Asthma Control Questionnaire (ACQ)

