4.4. Sample Size

An overall population size of 44 asthmatic subjects was based on the following assumptions:

- Type I error probability $\alpha = 5\%$
- Effect size = $(\mu_1 - \mu_0) / \sigma$
 - μ_i = mean PEP in group i ($i=1$: OC459, $i=0$: placebo),
 - σ = standard deviation of PEP
- PEP is primary end-point (=total daily lower respiratory symptom scores over D0 to D14, potential maximum of 315).

Based on a previously completed trial with similar design conducted at the same study site [10], σ is estimated to be 21.15 and the effect size equal to 22.21, yielding $n=15$ evaluable subjects per treatment group at 80% power. This is grossed-up for 80% rhinovirus inoculation success and adjusted for expected drop-outs to yield 22 enrolled patients per treatment group.

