7.2. Primary Analysis

Uncorrected lower respiratory symptom scores collected from D0 to D14 will be aggregated to create an overall total for each patient. Where patient scores are missing, data will be imputed based upon rules set within Section 7.5. Patients missing $\geq 20\%$ of score data will be excluded from any additional per-protocol analyses.

Data will be presented using summary statistics per treatment group and will include median and interquartile range (IQR). A supplementary plot showing individual measurements for both groups with a box & whisker overlay showing median and IQR will be produced.

Primary analysis to test for difference between the mean aggregated scores of the two treatment groups will be carried out using Mann-Whitney U tests. Differences will be considered significant at $P < 0.05$. All P values are two-sided.

An additional secondary analysis will take place correcting the scores for bronchoscopy-related symptoms. Full methodology will be clarified within Section 7.3.1 below.

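### The primary endpoint measures symptom level after three weeks on randomised drug, so a positive result alone cannot show that OC459 attenuates rhinovirus-induced deterioration

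*SAP*

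**What the plan says.** - Hypothesis (Protocol 1.2, repeated in SAP 4.1): "CRTH2 antagonism can prevent or attenuate the deterioration in symptoms in patients with asthma (i.e. asthma exacerbations) following rhinovirus infection".
- Treatment timing (Protocol 9.1): eligible subjects are randomised at baseline, "followed by a 21 day run-in period on placebo or OC459". Dosing then continues to Day 14.
- Primary endpoint (SAP 6.2): "The primary endpoint will consist of the sum of uncorrected lower respiratory symptom scores from day 0 to day 14". On scale: "Daily scores will be out of 21 (seven symptom questions rated from zero to three) creating a potential maximum total score of 315".
- Primary test (SAP 7.2): "Primary analysis to test for difference between the mean aggregated scores of the two treatment groups will be carried out using Mann-Whitney U tests". It is two-sided at P < 0.05 and has no covariate.
- Entry (Protocol 4.2): an ACQ score above 0.75, so subjects have some symptoms before inoculation.
- Baseline data (Protocol 9.4): daily diaries start on Day -21, and deriving a baseline symptom score is their stated purpose. The primary analysis does not use it.
- Corrected lower score (SAP 7.3.1): bronchoscopy-related symptoms are removed from Days 5 and 6, using the mean of Days -13 to -9 as reference. Background symptoms stay in the total.
- Deterioration measure (SAP 7.3.1): change from Day 0 to peak in symptoms, lung function and lung inflammation is a secondary efficacy analysis compared between arms. In Table 03 (SAP 7.4.4) this change is labelled a secondary outcome for PEFR, FEV₁ and FeNO. For the lower respiratory score it carries only an X, which the table's note defines as exploratory.

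**The concern.** Level and deterioration are different quantities, and this design lets them diverge. Suppose OC459 improves everyday asthma control during the run-in and does nothing to the response to virus. The active arm then starts Day 0 lower and stays lower by the same amount, and the primary total records that gap 15 times. Randomisation does not remove it, because the gap arises after randomisation. All subjects are to be inoculated and efficacy is analysed only in those infected (SAP 5.2), so no uninoculated group isolates the background effect.

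What is at stake is the claim. A significant total would validly show fewer symptoms on drug. It would not by itself support the stated hypothesis. Conversely, differences between subjects in background symptoms add noise that can hide a real effect on deterioration.

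**Working it through.** **Inputs.** SD 21.15, difference 22.21, 15 evaluable per arm, 80% power, alpha 5% (Protocol 10.1, SAP 4.4); two-sided test (SAP 7.2); 15 diary days (Day 0 to Day 14). The documents do not give the effect of OC459 on run-in symptoms, the background diary score, or the correlation between run-in and post-inoculation scores. These are assumed below.

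**1. The plan's own figure.** n per arm = 2(1.960 + 0.842)² / (22.21/21.15)² = 15.70/1.103 = 14.2, rounded up to 15. This matches. It works only with 22.21 read as a raw difference (standardised, 1.05), although the text labels it an effect size. Power at 15 per arm is 82% by the normal approximation, 79% by t-test and about 76% by simulated Mann-Whitney on normal data.

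**2. Per-day size.** 22.21/15 = 1.48 points per day on a 0-21 scale; half of that is 0.74.

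**3. Pure background effect.** Let OC459 lower every day's score by k, run-in included, with no effect on the virus-induced rise. The total shifts by 15k. The standard error is 21.15 × √(2/15) = 7.72, and the normal-approximation chance of significance is Φ(15k/7.72 − 1.96).

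| k (points/day) | shift in total | normal approx. | t-test | Mann-Whitney (simulated) |
|---|---|---|---|---|
| 0.25 | 3.75 | 7% | 8% | 6.5% |
| 0.50 | 7.5 | 16% | 16% | 14% |
| 0.74 | 11.1 | 30% | 28% | 26% |
| 1.00 | 15.0 | 49% | 47% | 42% |
| 1.48 | 22.2 | 82% | 79% | 76% |

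On a t-test with this SD, an observed difference of 2.048 × 7.72 = 15.8 points (1.05 per day) reaches P = 0.05.

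**4. Baseline-subtracted total.** Define it as the Day 0-14 total minus 15 × the mean daily score in an on-treatment, pre-inoculation window. A constant shift cancels: (total − 15k) − 15(mean − k) = total − 15 × mean. Simulated under k = 0.5, 1.0 and 1.48 (correlation 0.5, equal SDs), this endpoint is significant in about 4.5% of trials. The cancellation is complete only if the background effect is fully present in the window. If half of a 1.48-point effect develops later, 15 × 0.74 = 11.1 points remain.

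**5. Precision of that endpoint.** Its SD is 21.15 × √(1 + r² − 2ρr), where r is the ratio of baseline to post-inoculation SD and ρ their correlation. At r = 1 and ρ = 0.5 the SD is again 21.15, giving 15 per arm and 82% power for 22.21 points. Over r = 0.5 to 1.0 and ρ = 0.3 to 0.8, power at 15 per arm runs from 68% (SD 25.0) to above 99% (SD 12.7).

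**6. Would agreement in direction be enough?** No. With no effect on deterioration and the same ranges of r and ρ, the baseline-subtracted total still favours OC459 in roughly 54-65% of trials with a significant primary at k = 1.48, and in roughly 66-95% at k = 0.74. By contrast, a 95% interval excludes zero in favour of OC459 in only about half of 5%, that is 2.5%, of all such trials.

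**The case against.** The strongest reply is that the plan already covers much of this.

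- A reader might infer that deterioration in the lower score is measured only by an optional exploratory analysis. SAP 7.3.1 does not support that: change from Day 0 to peak in symptoms is planned there as secondary efficacy and tested between arms. Day 0 is on drug, so that change subtracts a run-in effect. What stands is that it rests on two single days, has conflicting status in Table 03, and governs no conclusion.
- Table 2.02 gives daily lower scores by arm from Day 0, and Tables 1.02 and 1.03 give ACQ-6, FEV₁ and FeNO at Day -21 and Day 0. A sizeable background effect would probably be visible. This is useful for interpretation, but no rule says what follows from it.
- The worded primary objective is identical to the endpoint, and the randomised comparison is valid. This is correct. The gap lies between the endpoint and the hypothesis, not between the endpoint and the objective. Nor does the SAP say that a positive total will be reported as attenuated deterioration.
- A reader might take the 76% as a false-positive rate. It is not: in that scenario the drug really does lower symptoms. It is the chance that a background effect alone produces a significant primary result.
- A reader might also see an inconsistency in Protocol 9.4, where the upper respiratory score has "the recording on the day prior to inoculation subtracted". That rule belongs to a six-day cold score. The SAP analyses the upper score as a Day 0-14 total and states no subtraction, so the two scores are treated alike.
- The background effect is assumed. An ACQ above 0.75 does not convert to diary points, and a fall of k per day needs at least k points of background to remove. Both limits stand.

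**Conclusion.** The point holds as a limit on what the primary result can show. The uncorrected total, the 21 days on drug before inoculation, the absence of a baseline term and the hypothesis about deterioration are all explicit. A positive primary alone therefore cannot separate an effect on background symptoms from an effect on the response to virus, and the planned Day 0-to-peak change only partly fills that gap.

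The size is conditional. With 15 per arm, SD 21.15, normal scores and a constant daily shift, background reductions of 0.74 and 1.48 points per day give a significant primary in about 26% and 76% of trials; the baseline-subtracted total stays near 5%. The larger shift equals the whole planned effect and is the upper illustration, not a prediction. The documents do not show that OC459 has a background effect of any particular size, and they do not support calling the primary comparison invalid.

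**What to change.** Leave the primary endpoint, test and sample size as they are.

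1. In SAP 6.3.1 and 7.3.1, name as first-listed secondary endpoint the Day 0-14 lower respiratory total minus 15 × the subject's mean daily score over Days -13 to -9. The SAP already uses this window, and it precedes bronchoscopy. It falls only 8 to 12 days after dosing starts, so add a sensitivity analysis with a later window nearer Day 0 and clear of Days -8 and -7, for example Days -5 to -1.
2. Compute it with and without the existing Day 5-6 bronchoscopy correction.
3. Report the between-arm difference with a 95% confidence interval (Hodges-Lehmann would match the Mann-Whitney test) and the run-in mean by arm.
4. Make Table 03 agree with SAP 7.3.1 on the status of the lower-score change from Day 0 to peak.
5. State in advance that a positive primary is reported as lower total symptom burden. Attenuated rhinovirus-induced deterioration is claimed only if the 95% interval for the baseline-subtracted total excludes zero in favour of OC459. Agreement in direction is not enough.

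The cost is SAP wording and a small number of tables from diaries already collected. The downsides are one more secondary endpoint, power for the stronger claim that depends on an unknown correlation, and a more restrained conclusion if the two results differ.
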